9.7 DATA ANALYSIS

The two cohorts will be analysed separately

- Uncommon mutations
- Sequencing of osimertinib after afatinib

The primary endpoint for both cohorts is time on treatment. Kaplan-Meier estimates will be calculated. In addition, the median will be tabulated along with the two-sided 95% confidence interval, using Greenwood's variance estimate.

The following additional endpoints will be analyzed similarly to the primary endpoint.

- overall survival
- time on treatment until failure of second-line (uncommon cohort only)

Patients who were not known to have discontinued treatment will be censored on the date they were last verified to have been on treatment.

A second round of data collection for additional follow-up may be performed in case a substantial proportion of patients had not discontinued treatment before the estimated median time on treatment at the time of the primary data collection.

Best overall response will be tabulated, as will the following:

- demographics
- disease characteristics
- methodology and material used for mutation classification
- anti-cancer drugs used prior to, or after EGFR-TKI (uncommon cohort only).

These endpoints will be analyzed descriptively.

Within the sequencing cohort, the proportion of patients with different types of resistance mutations observed at the time of discontinuation of osimertinib will be categorized and tabulated.

In this study, data will be gathered retrospectively from patients treated within the conditions of the approved marketing authorization of afatinib. Drug exposure during pregnancy, ADRs with causality to Gilotrif (serious or non-serious) and all fatal AEs will be reported to PV on the NIS AE form - excluding deaths to PD of the underlying malignancy. Safety data will be reviewed and analysed as part routine global pharmacovigilance procedures. All adverse events/reactions collected for the study per protocol will be summarised in the final study report.

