- For UNCOMMON MUTATION COHORT, it will be defined according to the fields **[First-line treatment period / MUT1. MUT1_unc, MUT1_unc_ex20_sp, MUT1_unc_sp]**.
- For SEQUENCING COHORT, it will be defined according to the field **[First-line treatment period / MUT1. MUT1_seq]**.

EGFR mutational status at second-line treatment start

It will be defined according to the following fields recorded in the MUTATIONS form of the [**Second-line treatment period**] time period (when applicable); for UNCOMMON MUTATION COHORT, only patients with Number of NSCLC treatment lines (as defined before) >1 should be considered:

- if “Was mutational status re-evaluated at start of second-line treatment?” [**MUT2. MUT2_reeval**] = “No” OR if “Any changes in EGFR mutations at start of second-line treatment with respect to start of first-line treatment?” [**MUT2. MUT2_changes**] = “UNK”, patients will be classified as “Unknown EGFR mutational status”
- if “Any changes in EGFR mutations at start of second-line treatment with respect to start of first-line treatment?” [**MUT2. MUT2_changes**] = “No”, then the patient’s EGFR mutational status at second-line treatment start will be imputed as the same patient’s EGFR mutational status at first-line treatment start (as defined before)
- if “Any changes in EGFR mutations at start of second-line treatment with respect to start of first-line treatment?” [**MUT2. MUT2_changes**] = “Yes”, then the patient’s EGFR mutational status at second-line treatment start will be retrieved from the fields [**MUT2. MUT2_mut_start**, **MUT2_mut_start_ex20_sp**, **MUT2_mut_start_sp**, **MUT2_concom_mut_start**]

Acquired EGFR mutations at second-line treatment start

For both cohorts, the mutations found at start of second-line treatment (i.e. the options selected in the field [**MUT2. MUT2_mut_start**]) will be compared to the mutations found at start of first-line treatment (i.e. the options selected in the field [**MUT1. MUT1_mut_unc**] for the UNCOMMON MUTATION COHORT, or in the field [**MUT1. MUT1_mut_seq**] for the SEQUENCING COHORT). The mutations found at start of second-line treatment that were not present at first-line treatment start will be classified as acquired EGFR mutations.

EGFR mutational status at second-line treatment stop/end of observation

It will be defined according to the following fields recorded in the MUTATIONS form of the [**Second-line treatment period**] time period (when applicable):

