- if “Was mutational status re-evaluated at at stop of second-line treatment (or within end of observation, in case second-line treatment was not discontinued)?” [**MUT2. MUT2_reeval_stop**] = “No” OR if “Any changes in EGFR mutations with respect to start of second-line treatment?” [**MUT2. MUT2_changes_stop**] = “UNK”, patients will be classified as “Unknown EGFR mutational status”
- if “Any changes in EGFR mutations with respect to start of second-line treatment?” [**MUT2. MUT2_changes_stop**] = “No”, then the patient’s EGFR mutational status at second-line treatment stop/end of observation will be imputed as the same patient’s EGFR mutational status at second-line treatment start (as defined before)
- if “Any changes in EGFR mutations with respect to start of second-line treatment?” [**MUT2. MUT2_changes_stop**] = “Yes”, then the patient’s EGFR mutational status at second-line treatment stop/end of observation will be retrieved from the fields [**MUT2. MUT2_mut_stop**, **MUT2_mut_stop_ex20_sp**, **MUT2_mut_stop_sp**, **MUT2_concom_mut_stop**]

Acquired EGFR mutations at second-line treatment stop/end of observation

For both cohorts, the mutations found at stop of second-line treatment/end of observation (i.e. the options selected in the field [**MUT2. MUT2_mut_stop**]) will be compared to the mutations found at start of second-line treatment (i.e. the options selected in the field [**MUT2. MUT2_mut_start**]). The mutations found at second-line treatment stop/end of observation that were not present at start of second-line treatment will be classified as acquired EGFR mutations.

Classification of EGFR uncommon mutations (according to Yang's classification) for exploratory analyses

According to the MUTATIONS form, considering the EGFR mutational status at first- and second-line treatment start (but considering only lines containing EGFR-TKIs), the following definitions will be applied to classify patients' mutational status with respect to EGFR gene:

- **T790M-positive:** patients having T790M at start of either first- or second-line EGFR-TKI, but excluding patients developing acquired T790M at second-line osimertinib start;
- **Exon 20 insertion-positive:** patients having any type of exon 20 insertion at start of either first- or second-line EGFR-TKI, excluding patients included in group "a");

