- **Major uncommon mutations:** patients having either G719X and/or L861Q and/or S768I mutations at start of either first- or second-line EGFR-TKI, excluding patients included in groups "a)" or "b");
- **Others:** patients not included in groups "a)", "b)", or "c");
- **Compound mutations:** patients having more than one mutation of any type (including also common mutations).

The same patient cannot be included in more than one of the following groups, which are mutually exclusive: a), b), c), d). On the contrary, the same patient can be included in group e) and also in another group a) or b) or c) or d).

Source: Chih-Hsin Yang J, Schuler M, Popat S, Miura S, Heeke S, Park K, Märten A, Kim ES, Afatinib for the Treatment of Non-Small Cell Lung Cancer Harboring Uncommon EGFR Mutations: A Database of 693 Cases, *Journal of Thoracic Oncology* (2020), doi: <https://doi.org/10.1016/j.jtho.2019.12.126>.

Classification of EGFR uncommon mutations at first-line treatment start

The same 5 classes described above will be considered, but considering only EGFR mutational status at first-line treatment start (see algorithm described before), and without restrictions on type of treatment line.

Classification of EGFR uncommon mutations at second-line treatment start

The same 5 classes described above will be considered, but considering only EGFR mutational status at second-line treatment start (see algorithm described before), and without restrictions on type of treatment line.

In particular, "T790M-positive" group includes also patients developing acquired T790M at second-line osimertinib start, while excludes patients with T790M acquired only and treated with osimertinib. However, if the patient had also additional acquired mutations at start of second-line osimertinib (and not only acquired T790M), then the patient will not be excluded.

Only patients with Number of NSCLC treatment lines (as defined before) > 1 and [**MUT2. MUT2_reeval**] = "Yes" will be considered.

Patients without mutations at second line treatment start will not be included in "Others".

Classification of EGFR uncommon mutations at second-line treatment stop/end of observation

The same 5 classes described above will be considered, but considering only EGFR mutational status at second-line treatment stop/end of observation (see algorithm described before), and without restrictions on type of treatment line.

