Number of NSCLC treatment lines	87
Number of NSCLC treatment lines	88
Number of NSCLC treatment lines	89
Number of NSCLC treatment lines	90
Number of NSCLC treatment lines	91
Number of NSCLC treatment lines	92
Number of NSCLC treatment lines	93
Number of NSCLC treatment lines	94
Number of NSCLC treatment lines	95
Number of NSCLC treatment lines	96
Number of NSCLC treatment lines	97
Number of NSCLC treatment lines	98
Number of NSCLC treatment lines	99
Number of NSCLC treatment lines	100

Table 12-UNC. Mutations at second-line treatment start (ELIGIBLE PATIENTS of the Uncommon Mutation Cohort)

The table will provide:

- absolute and relative frequency of patients according to EGFR mutational status at second-line treatment start (see “Computed variables” chapter);
- absolute and relative frequency of patients according to Classification of EGFR uncommon mutations at second-line treatment start (see “Computed variables” chapter);
- absolute and relative frequency of patients according to acquired EGFR mutations at second-line treatment start (see “Computed variables” chapter);
- absolute and relative frequency of patients according to presence/absence of other new mutated genes and detail of new mutations at second-line treatment start (according to the fields [*Second-line treatment period / MUT2. MUT2_oth_gene_start_YN (*)*, *MUT2_oth_gene_start, MUT2_oth_gene_start_sp*]).

(*) in case [*MUT2_oth_gene_start_YN*] = “No”, then the patient’s mutational status for other genes at second-line treatment start will be imputed as the same patient’s mutational status for other genes at first-line treatment.

Descriptives and percentages will be calculated over the number of ELIGIBLE PATIENTS in the cohort, considering only patients with Number of NSCLC treatment lines >1 (see “Computed variables” chapter).

Table 13-UNC. Approaches for detection of mutations at second-line treatment start (ELIGIBLE PATIENTS of the Uncommon Mutation Cohort) – Secondary objective #3

The table will provide:

- absolute and relative frequency of patients by “Biologic sample(s) used for mutation testing” (according to the fields [*Second-line treatment period / MUT2. MUT2_biol_samp, MUT2_biol_samp_sp*]);

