T790M-positive ELIGIBLE PATIENTS (N=xxx)	
Methodology used for mutation testing	
Amplification Refractory Mutation System (ARMS)	xxx (xx.x%)
ddPCR	xxx (xx.x%)
BEAMing	xxx (xx.x%)
...	...
Exon 20 insertion-positive ELIGIBLE PATIENTS (N=xxx)	
Methodology used for mutation testing	
Amplification Refractory Mutation System (ARMS)	xxx (xx.x%)
ddPCR	xxx (xx.x%)
BEAMing	xxx (xx.x%)
...	...
ELIGIBLE PATIENTS with Major uncommon mutations (N=xxx)	
Methodology used for mutation testing	
Amplification Refractory Mutation System (ARMS)	xxx (xx.x%)
ddPCR	xxx (xx.x%)
BEAMing	xxx (xx.x%)
...	...
Other (not included in the previous groups) ELIGIBLE PATIENTS (N=xxx)	
Methodology used for mutation testing	
Amplification Refractory Mutation System (ARMS)	xxx (xx.x%)
ddPCR	xxx (xx.x%)
BEAMing	xxx (xx.x%)
...	...

ELIGIBLE PATIENTS with Compound mutations (N=xxx)	
Methodology used for mutation testing	
Amplification Refractory Mutation System (ARMS)	xxx (xx.x%)
ddPCR	xxx (xx.x%)
BEAMing	xxx (xx.x%)
...	...

Table 12-UNC. Mutations at second-line treatment start (ELIGIBLE PATIENTS of the Uncommon Mutation Cohort)

ELIGIBLE PATIENTS with >1 NSCLC line (N=xxx)		
EGFR mutational status at second-line treatment start	Del19	xxx (xx.x%)
	L858R	xxx (xx.x%)
	L858X (with X being unequal to R)	xxx (xx.x%)
	T790M de novo	xxx (xx.x%)
	G719X	xxx (xx.x%)
	L861Q	xxx (xx.x%)
	S768I	xxx (xx.x%)
	E709X	xxx (xx.x%)
	L747P/S	xxx (xx.x%)
	Q787Q	xxx (xx.x%)
	Exon 20 insertion (*)	xxx (xx.x%)
	Other EGFR mutation(s) (*)	xxx (xx.x%)
	Unknown EGFR mutational status	xxx (xx.x%)
Classification of EGFR uncommon mutations at second-line treatment start	T790M-positive	xxx (xx.x%)
	Exon 20 insertion-positive	xxx (xx.x%)
	Major uncommon mutations	xxx (xx.x%)
	Others	xxx (xx.x%)
	Compound mutations	xxx (xx.x%)

(*) listing might be provided depending on the number of cases observed.

ELIGIBLE PATIENTS with >1 NSCLC line (N=xxx)		
Acquired EGFR mutations at second-line treatment start	Del19	xxx (xx.x%)
	L858R	xxx (xx.x%)

ELIGIBLE PATIENTS with >1 NSCLC line (N=xxx)		
Other new genes alterations at start of second-line treatment?	Yes	xxx (xx.x%)
	No	xxx (xx.x%)
	UNK	xxx (xx.x%)
Other known genes alterations	ALK	xxx (xx.x%)
	HER2	xxx (xx.x%)
	KRAS	xxx (xx.x%)
	MET amplification	xxx (xx.x%)
	PI3KCA	xxx (xx.x%)
	PTEN	xxx (xx.x%)
	ROS1	xxx (xx.x%)
	Other gene(s) mutated (*)	xxx (xx.x%)

(*) listing might be provided depending on the number of cases observed.

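### Table 12-UNC divides class and acquired-mutation counts by a total that includes patients never re-tested, and Table 13-SEQ does not match the discontinuation time point in Protocol 9.7

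*SAP*

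**What the plan says.** **Table 12-UNC.** SAP 4.1.3 lists several blocks for this table, among them the EGFR status, the uncommon-mutation class, and "absolute and relative frequency of patients according to acquired EGFR mutations at second-line treatment start". One sentence sets the denominator for all of them: "percentages will be calculated over the number of ELIGIBLE PATIENTS in the cohort, considering only patients with Number of NSCLC treatment lines >1". The layout in SAP 5.1.3 repeats it in the block headers ("ELIGIBLE PATIENTS with >1 NSCLC line (N=xxx").

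SAP 3 defines the variables behind these blocks:

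- A patient who was not re-evaluated at second-line start, or whose change status is unknown, gets "Unknown EGFR mutational status".
- Acquired mutations need a second-line result: "The mutations found at start of second-line treatment that were not present at first-line treatment start will be classified as acquired EGFR mutations".
- The class at second-line start has its own restriction: "Only patients with Number of NSCLC treatment lines (as defined before) > 1 and", and the sentence goes on to require MUT2_reeval = Yes.

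The neighbouring tables add the filter that Table 12-UNC lacks. In SAP 4.1.3, the text for Table 13-UNC requires MUT2_reeval = Yes and the text for Table 15-UNC requires MUT2_reeval_stop = Yes.

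**Table 13-SEQ.** For the afatinib-osimertinib patients, Protocol 9.7 states that "the proportion of patients with different types of resistance mutations observed at the time of discontinuation of osimertinib will be categorized and tabulated". SAP 4.2.3 titles the table as osimertinib stop or end of observation and refers to the corresponding uncommon-cohort table, which by title is Table 15-UNC. The re-evaluation field used there also covers a test done "or within end of observation, in case second-line treatment was not discontinued" (SAP 3).

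**The concern.** A percentage is readable only if everyone in the denominator could have appeared in the numerator. In Table 12-UNC, patients not re-tested at second-line start have no second-line result, so they can add to the denominator of the class and acquired rows but never to the numerator. The printed figure then moves with how often sites re-test, as well as with what the tests find. It also cannot be set beside Table 15-UNC, which reports the same kind of variable at a later time point over re-tested patients only.

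In Table 13-SEQ the issue is the time point. The protocol asks what is found when osimertinib is stopped. The SAP mixes in patients tested while still taking it, so a reader looking for the profile at discontinuation gets a different population.

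**Working it through.** The documents give no expected acquired-mutation percentage and no re-test rate, so there is no plan figure to reproduce. The check compares the rules and works through the denominators.

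**1. Table 12-UNC, block by block**

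| Block | Can an untested patient be in a numerator? | Stated denominator | Layout row for untested patients |
|---|---|---|---|
| EGFR status | Yes, as unknown | >1 line | Yes |
| Class | No (MUT2_reeval = Yes needed) | >1 line | None among the five classes |
| Acquired EGFR | No (second-line result needed) | >1 line | None shown; the shell lists only Del19 and L858R |

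Only the status block is coherent. Four of the five classes are mutually exclusive, so their percentages together cannot exceed the share re-tested.

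**2. Size in Table 12-UNC**

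Let N be the patients with more than one line, r the share re-tested with known change status, and p the proportion of those with a given acquired mutation. The count is N × r × p. The printed percentage is N × r × p / N = p × r. With the denominator N × r it would be p.

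| p | r = 0.3 | r = 0.5 | r = 0.7 | r = 0.9 |
|---|---|---|---|---|
| 24% | 7.2% | 12.0% | 16.8% | 21.6% |
| 50% | 15.0% | 25.0% | 35.0% | 45.0% |
| 66% | 19.8% | 33.0% | 46.2% | 59.4% |

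The values 24% and 66% are the T790M positivity rates by two assays in Protocol 7.2, borrowed only to span a range. The 50% and every r are assumptions.

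Table 11-SEQ follows Table 12-UNC but does not have this problem for EGFR: SAP 2.1 criterion 6 requires T790M in the second-line mutation field, so r = 1 there.

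**3. Table 13-SEQ**

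Let c be the share of patients still on osimertinib, k their re-test rate relative to discontinued patients, and p and q the proportions with a new mutation among re-tested discontinued and re-tested ongoing patients. Then

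printed = [p(1 − c) + q·c·k] / [(1 − c) + c·k].

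If q = p nothing changes; q below p lowers the figure and q above p raises it. The documents give neither q nor k. The extreme q = 0, with p = 50%, gives a floor:

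| c | k = 0.1 | k = 1 |
|---|---|---|
| 10% | 49.5% | 45.0% |
| 30% | 47.9% | 35.0% |
| 48% | 45.8% | 26.0% |

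The 10% and 30% are censoring levels from Protocol 9.5. The 48% is 100% − 52%, from the maturity of the earlier real-world study in Protocol 7.2. With k = 0 there is no effect. These are limits under q = 0 and should not be read as estimates.

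**4. Table 15-UNC layout**

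Its header in SAP 5.1.3 omits the re-evaluated restriction that its text in SAP 4.1.3 imposes. If programming follows the header, patients never re-tested enter Table 13-SEQ as well. Assuming 60% of discontinued patients are re-tested and q = 0, a proportion of 50% would print as 0.50 × (1 − c) × 0.6 = 27.0%, 21.0% and 15.6% for c = 10%, 30% and 48%.

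**The case against.** **The general missing-data rule.** SAP 4 excludes patients with missing data from the analysis of the variable concerned, which could be read as removing untested patients from the acquired rows. This has force: the SAP nowhere says that an untested patient counts as having acquired nothing. But not being re-tested is a recorded answer mapped to a defined category, the status block prints that category over the full N, and Table 12-UNC states its own denominator. The rules conflict, and neither clearly overrides the other.

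**The shell and the reader.** The acquired block in the layout is evidently abbreviated (T790M is not even listed), so the absence of an unknown row there proves little. Counts are unaffected, and Table 13-UNC gives the number re-evaluated, so a careful reader could recompute the percentage. Both points stand; they limit the harm but leave the stated denominator as it is.

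**Stronger readings to avoid.** A reader might infer that patients still on osimertinib could not show a resistance mutation, so that Table 13-SEQ must understate resistance. The documents do not support this: the inherited text counts only re-tested patients, and SAP 3 records new mutations found on treatment. A reader might also take the corrected Table 12-UNC figure as the biological rate of acquired T790M after a first TKI. It is not, because re-tested patients are a selected group and first-line treatment could be chemotherapy or another therapy.

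**What cannot be checked.** SAP 4.2.7 is blank in the public copy and the revision history mentions a Table 27-SEQ that is not shown, so another table may cover discontinuation alone. Table 13-SEQ itself does not.

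**Conclusion.** The Table 12-UNC point holds. The stated denominator is at odds with the class rule in SAP 3 and with the text of Tables 13-UNC and 15-UNC. It scales the acquired percentages by the re-test share, so half re-tested means half the percentage. That share is assumed throughout.

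For Table 13-SEQ, what holds is a mismatch with Protocol 9.7. Dilution is plausible, but neither its direction nor its size can be established from the documents, and it is small if few patients were re-tested on treatment.

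The consequence is moderate. Both tables are descriptive and carry no objective tag, and no primary or secondary estimate changes. It is still worth correcting, because the stated rules would print percentages that do not mean what their labels suggest.

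**What to change.** 1. **Table 12-UNC:** calculate the class and acquired-mutation percentages over patients with more than one line, MUT2_reeval = Yes and MUT2_changes known. Show the number not re-tested, and the number with unknown change status, outside that denominator. Keep the status block as it is.
2. **Footnote to Table 12-UNC:** state that re-tested patients are a selected group and that first-line treatment was not always an EGFR-TKI.
3. **Table 13-SEQ:** make patients with OAD_treat_disc = Yes and MUT2_reeval_stop = Yes the main column, and show patients re-tested while still on osimertinib in a separate column. Table 22-SEQ already restricts to patients who discontinued. Discontinuation includes stops for reasons other than progression (Protocol 9.3 collects the reason), so label the column as discontinuation.
4. **Table 15-UNC layout:** add the re-evaluated restriction to the header so that it agrees with the text.
5. **SAP 4:** state how the general missing-data rule relates to table-specific denominators.

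All fields are already collected, so the work is SAP wording and programming. The cost is smaller denominators and less precise percentages.

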4.1.4 NSCLC treatments

Table 18-UNC. NSCLC treatment patterns (ELIGIBLE PATIENTS of the Uncommon Mutation Cohort)

The table will provide:

- patients' distribution (absolute and relative frequency) by Number of NSCLC treatment lines (see "Computed variables" chapter);
- patients' distribution (absolute and relative frequency) by type of NSCLC treatment patterns (see "Computed variables" chapter);

Descriptives and percentages will be calculated over the number of ELIGIBLE PATIENTS in the cohort.

Table 19-UNC. First-line treatment details (ELIGIBLE PATIENTS of the Uncommon Mutation Cohort)

The table will provide:

- absolute and relative frequency of patients by type of treatment (according to the field [*First-line treatment period / TREAT. TREAT_ty, TREAT_ty_sp*]); "Immune check-point inhibitors" and "Other immunotherapy" will be grouped together;
- absolute and relative frequency of patients by type of chemotherapy [*First-line treatment period / TREAT. TREAT_chemo, TREAT_chemo_sp*]); drug combinations will be shown in case of polychemotherapy regimens;
- absolute and relative frequency of patients undergoing radiotherapy (according to the field [*First-line treatment period /TREAT. TREAT_radio_YN*]);
- absolute and relative frequency of patients by type of targeted therapy (according to the field [*First-line treatment period /TREAT. TREAT_targTer, TREAT_targTer_sp*]);
- absolute and relative frequency of patients by type of immunotherapy (according to the field [*First-line treatment period /TREAT. TREAT_immuno, TREAT_immuno_sp*]).

Descriptives and percentages will be calculated over the number of ELIGIBLE PATIENTS in the cohort.

[figure not shown]

Table 22-UNC. First-line treatment regimen (ELIGIBLE PATIENTS of the Uncommon Mutation Cohort)

According to data distribution, it will be evaluated the opportunity to provide the absolute and relative frequency of patients by type of treatment (according to the field [*First-line treatment period / TREAT. TREAT_ty, TREAT_ty_sp*]) after having concatenated multiple options, in order to provide the frequency of combined treatments.

Descriptives and percentages will be calculated over the number of ELIGIBLE PATIENTS in the cohort.

Table 24-UNC. Response to first-line treatment (ELIGIBLE PATIENTS of the Uncommon Mutation Cohort) – Secondary objective #1

The table will provide:

- absolute and relative frequency of “Best response achieved” [*First-line treatment period / RESP. RESP_best*]
- absolute and relative frequency of patients achieving Overall Response (ORR), ie. those with [*First-line treatment period / RESP. RESP_best*] = “Complete response (CR)” or “Partial Response (PR)”;
- descriptive statistics (mean, standard deviation, quartiles, min, max) of Duration of response (in months) [*First-line treatment period / RESP. RESP_dur_num, RESP_dur_unit*] for patients achieving Overall Response (ORR) (as defined before); all units will be reported to months.

Descriptives and percentages will be calculated over the number of ELIGIBLE PATIENTS in the cohort, unless differently specified..

Table 25-UNC. Second-line treatment details (ELIGIBLE PATIENTS of the Uncommon Mutation Cohort)

The table will provide:

- absolute and relative frequency of patients by type of treatment (according to the field [*Second-line treatment period / TREAT. TREAT_ty, TREAT_ty_sp*]), “Immune check-point inhibitors” and “Other immunotherapy” will be grouped together;
- absolute and relative frequency of patients by type of chemotherapy [*Second-line treatment period / TREAT. TREAT_chemo, TREAT_chemo_sp*]]; drug combinations will be shown in case of polychemotherapy regimens;
- absolute and relative frequency of patients undergoing radiotherapy (according to the field [*Second-line treatment period /TREAT. TREAT_radio_YN*]);
- absolute and relative frequency of patients by type of targeted therapy (according to the field [*Second -line treatment period /TREAT. TREAT_targTer, TREAT_targTer_sp*]);
- absolute and relative frequency of patients by type of immunotherapy (according to the field [*Second -line treatment period /TREAT. TREAT_immuno, TREAT_immuno_sp*]).

Descriptives and percentages will be calculated over the number of ELIGIBLE PATIENTS in the cohort, considering only patients with Number of NSCLC treatment lines >1 (see “Computed variables” chapter).

Table 28-UNC. Second-line treatment regimen (ELIGIBLE PATIENTS of the Uncommon Mutation Cohort)

According to data distribution, it will be evaluated the opportunity to provide the absolute and relative frequency of patients by type of treatment (according to the field [*Second-line treatment period / TREAT. TREAT_ty, TREAT_ty_sp*]) after having concatenated multiple options, in order to provide the frequency of combined treatments. Descriptives and percentages will be calculated over the number of ELIGIBLE PATIENTS in the cohort, considering only patients with Number of NSCLC treatment lines >1 (see “Computed variables” chapter).

Table 30-UNC. Response to second-line treatment (ELIGIBLE PATIENTS of the Uncommon Mutation Cohort) – Secondary objective #1

The table will provide:

- absolute and relative frequency of “Best response achieved” [*Second-line treatment period / RESP. RESP_best*]
- absolute and relative frequency of patients achieving Overall Response (ORR), ie. those with [*Second -line treatment period / RESP. RESP_best*] = “Complete response (CR)” or “Partial Response (PR)”;
- descriptive statistics (mean, standard deviation, quartiles, min, max) of Duration of response (in months) [*Second -line treatment period / RESP. RESP_dur_num, RESP_dur_unit*] for patients achieving Overall Response (ORR) (as defined before); all units will be reported to months.

Descriptives and percentages will be calculated over the number of ELIGIBLE PATIENTS in the cohort, considering only patients with Number of NSCLC treatment lines >1 (see “Computed variables” chapter), unless differently specified.

Table 32-UNC. Index-line treatment regimen (ELIGIBLE PATIENTS of the Uncommon Mutation Cohort)

According to data distribution, it will be evaluated the opportunity to provide the absolute and relative frequency of patients by type of treatment (according to the fields **[First-line treatment period or Second-line treatment period / TREAT. TREAT_ty, TREAT_ty_sp]**, depending on which is the index-line) after having concatenated multiple options, in order to provide the frequency of combined treatments.

Descriptives and percentages will be calculated over the number of ELIGIBLE PATIENTS in the cohort.

Table 33-UNC. NSCLC treatments prior to index EGFR-TKI therapy patterns (ELIGIBLE PATIENTS of the Uncommon Mutation Cohort)

The table will provide:

- patients' distribution (absolute and relative frequency) by number of NSCLC lines prior to the index EGFR-TKI therapy (that will be obtained considering the ordinal number of the index EGFR-TKI therapy, as defined in the "Computed variables" chapter);
- patients' distribution (absolute and relative frequency) by pattern of NSCLC treatment prior to the index EGFR-TKI therapy (see "Computed variables" chapter) considering only the sequence of NSCLC treatments until the index EGFR-TKI therapy (excluded).

Descriptives and percentages will be calculated over the number of ELIGIBLE PATIENTS in the cohort.

Table 34-UNC. Index EGFR-TKI therapy patterns (ELIGIBLE PATIENTS of the Uncommon Mutation Cohort)

The table will provide:

- patients' distribution (absolute and relative frequency) by ordinal number of line of the index EGFR-TKI therapy (see "Computed variables" chapter);
- patients' distribution (absolute and relative frequency) by type of NSCLC treatment patterns (see "Computed variables" chapter) considering only the sequence of NSCLC treatments from the index EGFR-TKI therapy thereafter.

Descriptives and percentages will be calculated over the number of ELIGIBLE PATIENTS in the cohort.

Table 35-UNC. Response to index EGFR-TKI treatment (ELIGIBLE PATIENTS of the Uncommon Mutation Cohort) – Secondary objective #1

The table will provide:

- absolute and relative frequency of "Best response achieved" [**First-line treatment period or Second-line treatment period / RESP. RESP_best**, depending on which is the index-line];
- absolute and relative frequency of patients achieving Overall Response (ORR), ie. those with [**First-line treatment period or Second-line treatment period / RESP. RESP_best**] = "Complete response (CR)" or "Partial Response (PR)";
- descriptive statistics (mean, standard deviation, quartiles, min, max) of Duration of response (in months) [**First-line treatment period or Second-line treatment period / RESP. RESP_dur_num, RESP_dur_unit**] for patients achieving Overall Response (ORR) (as defined before); all units will be reported to months.

Descriptives and percentages will be calculated over the number of ELIGIBLE PATIENTS in the cohort, unless differently specified.

